2.4.5.4 Analyses of vital sign variables

The baseline value of all vital sign variables is the original baseline from the parent study. The pre-dose measurement at Week 0 of LTS14424 will be separately presented in the summaries or plots over time.

The summary statistics (including number, mean, median, standard deviation, Q1, Q3, minimum and maximum) of all vital signs variables (measurements and changes from baseline) will be calculated for each visit or study assessment (baseline, each post-baseline time point, and endpoint) for each analysis set ([Section 2](#)) of safety population by the treatment category. For all vital sign variables, the mean change from baseline with corresponding standard error at each visit will be plotted for each analysis set of safety population by the treatment category.

For all vital sign variables, the summary statistics over visits for either measurements or mean change from baseline, and the plot of mean change from baseline over visits should include the measurements obtained at either scheduled or unscheduled visits.

The incidence of PCSAs (list provided in [Appendix A](#)) at any time during the treatment-emergent adverse event period as defined in [Section 2](#) will be summarized for each analysis set of safety population by the treatment category irrespective of the baseline level and/or according to the following status at baseline of parent study and at Week 0 of LTS14424 study, respectively:

- Normal/missing.
- Abnormal according to PCSA criterion or criteria.

For PCSA analyses, the vital sign measurements obtained at either scheduled or unscheduled visits should be used.

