4 INTRODUCTION AND RATIONALE

4.1 INTRODUCTION

Asthma is the most common chronic lung disease of childhood that affects >6.6 million children in the United States (US). Asthma is a chronic inflammatory disease of the airways characterized by airway hyper-responsiveness, acute and chronic bronchoconstriction, airway edema, and mucus plugging. The inflammatory component of asthma involves many cell types, including mast cells, eosinophils, T-lymphocytes, neutrophils, and epithelial cells and their biological products. For most asthma patients, a regimen of controller therapy and reliever therapy provides adequate long-term control.

The majority of children with asthma have mild or moderate disease and can obtain adequate asthma control through avoidance of triggering factors and/or with the help of medications, such as short acting inhaled β 2-receptor agonists, inhaled corticosteroids (ICS) and, when needed, addition of long acting β 2-receptor agonists and leukotriene receptor antagonists (LTRA). However, 2% to 5% of all asthmatic children have uncontrolled asthma despite maximum treatment with conventional medication (1). Children with such severe symptoms are heterogeneous with respect to trigger factors, pulmonary function, inflammatory pattern, and clinical symptoms (2). These children have a reduced quality of life, account for a large proportion of the healthcare costs related to asthma and represent a continuous clinical challenge to the pediatrician. Additionally, the long-term adverse effects of systemic and ICS on bone metabolism, adrenal function, and growth in children lead to attempts to minimize the amount of corticosteroid usage. Lastly, the consequences of unresponsiveness to therapy or lack of compliance with therapy are evidenced by loss of asthma control (LOAC), which can be severe (that is severe asthma exacerbation event) and possibly life-threatening. The poor response of some patients with asthma may reflect the number of cellular and molecular mechanisms operative in asthma. There is increasing interest in distinct phenotypes because targeted therapy is more likely to be successful in patients with similar underlying pathobiologic features (3). Recent therapeutic approaches in asthma have been focused on trying to control type 2 inflammation.

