8.2 NONINVESTIGATIONAL MEDICINAL PRODUCT(S)

8.2.1 Inhaled corticosteroids alone or in combination with a second controller

The recognized second controller medication for combined use with ICS (dose-levels in children 7 to 12 years old) as background therapy during this study will include the following classes: LABA, LTRA, Long acting muscarinic antagonist (LAMA), or methylxanthines. Please refer to [Section 17.1](#) for an indicative (not exhaustive) list of recognized second controller medications approved for this study. These controller medications will not be dispensed or supplied by the Sponsor.

Route of administration:

- Oral inhalation via metered dose inhaler (MDI) or dry powder inhaler (DPI) (for example ICS, ICS combination, albuterol/salbutamol, etc); for other background controllers according to label that is applicable to pediatric patients.

Dose regimen:

- Inhaled corticosteroids: ICS alone or in combination with a second controller as prescribed, as per Investigator's judgement.

For patients experiencing a deterioration of asthma during the study, the ICS with/without second controller dose may temporarily be increased, as indicated and upon recommendation of the physician and/or Investigator. Treatment may then be changed to systemic corticosteroid (SCS) (severe exacerbation event) or reverted back to the original ICS with/without second controller dose or modified ICS with/without second controller dose depending on the asthma symptoms progression.

At enrollment:

At enrollment, patients must be on background therapy (ICS alone or with a second controller) as in EOT visit of parent study. Patients enrolling into Study LTS14424 at a later date due to COVID-19 pandemic, must be on background therapy (High ICS dose alone or with a second controller or Medium ICS dose with a second controller).

If patients take 2 different ICS, the total daily dose of ICS should be calculated, to evaluate the daily dose of ICS.

Open-label treatment period:

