Laboratory tests, vital signs, physical examination, or electrocardiogram (ECG) abnormalities are to be recorded as AEs only if they meet the criteria defined in [Section 10.4.3](#), and are assessed as described in [Section 17.7.2.8.3.5](#), [Section 17.7.2.8.3.2](#), [Section 9.1.2](#) and [Section 17.7.2.8.3.4](#). In addition to assessment of primary endpoint, below parameters are used on an ongoing basis during the study to monitor safety of participants and will be presented in a descriptive manner.

17.7.2.8.3.2 Vital signs

Vital signs including blood pressure (mmHg), heart rate (beats per minute), respiratory rate (breaths per minute), and body temperature (degrees Celsius) will be measured at each onsite visit except for IMP administration only visits.

Vital signs will include height (cm) and body weight (kg). Height will be measured at each onsite visit except for the IMP administration only visit and Visit 9 (Week 36). Weight will be measured at each onsite visit except for the IMP administration only visit.

17.7.2.8.3.3 Physical examinations

See [Section 9.1.2](#).

17.7.2.8.3.4 Electrocardiograms

Electrocardiogram (ECG) variables will be recorded by a standard 12-lead ECG. ECGs will be performed at screening, EOT, and EOS (see [Section 17.7.2.2.2](#)).

17.7.2.8.3.5 Clinical laboratory values

Abnormal laboratory values that are considered to be clinically significant by the Investigator should be repeated as soon as possible after receiving the laboratory report to rule out laboratory error. Persistent abnormal laboratory values should be repeated until they return to normal or until an etiology of the persistent abnormality is determined.

Globally, guidelines for blood collection volume limits for pediatric studies range between 1% and 5% of total blood volume (TBV) for a single draw (or during a 24-hour period) and up to 10% of TBV over 8 weeks [\(9\)](#). Scheduled collections in the current protocol, for the smallest possible patient (15 kg), remain within this limit for every 3 months. For all scheduled blood collection visits, the total volume does not exceed 1.5 mL/kg for the smallest possible patient.

Refer to [Section 17.7.2.2.2](#) for the description of the clinical laboratory evaluations and the schedule of laboratory evaluations performed throughout this study. The clinical laboratory parameters that will be measured in safety are:

Hematology:

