2.1.4.4 Vital signs variables

Vital signs include blood pressure (mmHg), heart rate (beats per minute), respiratory rate (breaths per minute), body temperature (degrees Celsius) and body weight (kg) will be measured at every scheduled visit. Height (cm) will be measured at Visit 1 (Week 0) and Visit 10 (Week 52/EOT). Baseline values for vital signs will be the original baseline from the parent study.

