| | 6 to <12 years old (Children) | < 18 per minutes > 30 per minutes | |
| | 12 to 16/18 years old (Adolescents) | < 12 per minutes > 20 per minutes | |
| SaO2 | All age ranges | ≤ 95 % | |
| Weight | All ranges | ≥ 5 % weight loss from baseline | Based on identification of trends in the child's growth with a series of visits WHO Multicentre Reference Study Group, 2006; Center for Disease Control. Growth chart 2007 |

**CRITERIA for POTENTIALLY CLINICALLY SIGNIFICANT ABNORMALITIES
For Studies in Children**

| Parameter | Age range | PCSA | Comments |
|---------------------------|----------------|-------------------------------------------------------------------------------------------------------------|----------------------------------------------------------------------------------------------------------------------------------------------------------------------------------------------------------------------------------------------------------------------------------------------------------------------------------------------|
| Clinical Chemistry | | | Ref Molleston JP et al. JPN 2011; Moritz et al., Pediatrics 1999; Moritz et al., Pediatr Nephrol 2005 ; Sedlacek et al., Seminars in Dialysis 2006) Gong G et al. Clinical Biochemistry 2009; Masilamani et al. Arch Dis Children 2012; Mulberg AE et al. Pediatric Drug Development Concepts and applications. John Wiley & sons, Inc. 2009 |
| ALT/SGPT | All age ranges | ≥ 3 ULN By distribution analysis: ≥ 3 ULN ≥ 5 ULN ≥ 10 ULN ≥ 20 ULN | Based on normal ranges: 6 to 50 U/L (0-5 days), 5 to 45 U/L (1-19 years) |
| AST/SGOT | All age ranges | ≥ 3 ULN By distribution analysis: ≥ 3 ULN ≥ 5 ULN ≥ 10 ULN ≥ 20 ULN | Based on normal ranges: 35 to 140 U/L (0-5 days), 15 to 55 U/L (1-9 years), 5 to 45 U/L (10-19 years) |
| Alkaline Phosphatase | All age ranges | ≥ 1.5 ULN | Based on normal ranges: 145 to 420 U/L (1-9 years), 130 to 560 U/L (10-11 years), 200 to 495 U/L (Boys 12-13 years), 105 to 420 U/L (Girls 12-13 years), 130 to 525 U/L (Boys 14-15 years), 70 to 130 U/L (Girls 14-15 years), 65 to 260 U/L (Boys 16-19 years), 50 to 130 U/L (Girls 16-19 years) |
| Total Bilirubin | All age ranges | ≥ 1.3 ULN | $CF = mg \times 1.7 = \mu mol$ Based on normal ranges: <6 mg/dL (Term 0-1 day), <8 mg/dL (Term 1-2 days), <12 mg/dL (Term 3-5 days), <1 mg/dL (Term >5 days) |

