3.5.3 Additional safety assessments

3.5.3.1 Laboratory variables, vital signs and electrocardiograms (ECGs)

The following laboratory variables, vital signs and electrocardiogram (ECG) variables will be analyzed. They will be converted into standard international units.

- Hematology:
 - Red blood cells and platelets and coagulation: erythrocytes, hemoglobin, hematocrit, platelet count
 - White blood cells: leukocytes, with five-part differential count (neutrophils, lymphocytes, monocytes, basophils, eosinophils)
- Clinical chemistry:
 - Metabolism: glucose, total cholesterol, total protein, creatine phosphokinase (CPK), albumin
 - Electrolytes: sodium, potassium, chloride, bicarbonate
 - Renal function: creatinine, blood urea nitrogen
 - Liver function: alanine aminotransferase (ALT), aspartate aminotransferase (AST), alkaline phosphatase (ALP), total bilirubin
- Vital signs: systolic and diastolic blood pressure, heart rate, respiratory rate, body temperature, body weight, height.
- ECG variables: heart rate, PR, QRS, QRS axis, QT, QTc, RR.

Data below the lower limit of quantitation/detection limit (LLOQ) will be replaced by half of the LLOQ, data above the upper limit of quantification will be replaced by ULOQ value.

Quantitative analyses

When relevant, for laboratory variables, vital signs and ECG variables above, descriptive statistics for results and changes from baseline will be provided for each analysis window, the last value and the worst value (minimum and/or maximum value depending on the parameter) during the on-treatment period. These analyses will be performed using central measurements only for laboratory variables.

For each continuous parameter for laboratory variables and vital signs, mean change from baseline with corresponding standard error will be plotted over time.

Analyses according to PCSA

Potentially clinically significant abnormality (PCSA) analyses will be performed based on the PCSA list currently in effect at Sanofi at the time of the database lock. For parameters for which no PCSA criteria are defined, similar analyses will be done using the normal range, if applicable.

Analyses according to PCSA will be performed based on the worst value during the treatment-emergent period, using all measurements (either local or central, either scheduled, nonscheduled or repeated).

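### Main SAP 2.4.5.4 reports height only in raw centimetres from the parent-study baseline, so modest slowing of growth during the LTS14424 year is unlikely to be recognised

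*SAP*

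**What the plan says.** - **Background.** Protocol 4.1 refers to "the long-term adverse effects of systemic and ICS on bone metabolism, adrenal function, and growth in children". Protocol 8.2.1 makes inhaled steroid a condition of entry: "At enrollment, patients must be on background therapy (ICS alone or with a second controller) as in EOT visit of parent study". The investigator may later change the dose, and systemic steroids are allowed (8.2.3).
- **Collection.** In the main study height is scheduled at Week 0 and Week 52 (main SAP 2.1.4.4). A parent-baseline height is also held (2.1.1).
- **Baseline.** Main SAP 2.4.5.4: "The baseline value of all vital sign variables is the original baseline from the parent study". The Week 0 value is shown separately.
- **Summaries.** The same section plans descriptive statistics for values and for change from baseline by treatment category, and "For all vital sign variables, the mean change from baseline with corresponding standard error at each visit will be plotted".
- **Not planned.** The main SAP has no change from Week 0, annualised velocity, standardised height, abnormality criterion for height, or height by age or sex. The safety subgroups in 2.4.5.6 cover adverse-event variables only and do not include age.
- **Japan substudy.** Japan SAP 3.5.3.1 also lists height among the vital signs and summarises values and change. Its baseline is its own pre-dose value (3.1).

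**The concern.** In growing children a raw height change is positive whether growth is normal or somewhat slow. Its expected size depends on age, sex, pubertal stage and elapsed time. The planned table fixes none of these. It mixes the parent year with the LTS14424 year, pools children aged 7-9 with those aged 10 and above, and has no untreated group in the LTS14424 year to show what gain to expect. The SAP does standardise another size-dependent measure: lung function is reported as % predicted as well as in absolute units (2.1.3).

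At stake is whether the year of observation this study adds can say anything useful about growth. The children were on inhaled steroid at entry, and the protocol itself lists growth among the long-term harms of steroids.

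**Working it through.** The documents give no height SD, expected velocity or size of slowing. Every growth figure below is an **assumption** shown as a range.

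**1. Sample size behind the summary.** 0.87 × 408 = 354.96; both documents state approximately 354.

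**2. Precision in cm.** Half-width of the 95% CI = t × SD/√n. With an assumed SD of change of 1-3 cm and n = 354, it is 0.10-0.31 cm. Precision is adequate. What the table lacks is an expected value to compare with.

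**3. Time base.** Parent year plus LTS14424 year = 52 + 52 = 104 weeks. At 5-6 cm/year the reported change is about 10-12 cm. Assume slowing of 0.5-1.0 cm, confined to the LTS14424 year:

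| Slowing | Velocity | Share of LTS14424-year gain | Share of 104-week change |
|---|---|---|---|
| 0.5 cm | 5 cm/year | 10.0% | 5.0% |
| 0.5 cm | 6 cm/year | 8.3% | 4.2% |
| 1.0 cm | 5 cm/year | 20.0% | 10.0% |
| 1.0 cm | 6 cm/year | 16.7% | 8.3% |

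Measuring from the parent baseline halves the visible share.

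**4. Unequal follow-up.** Late entrants may start up to 12 weeks after the parent end-of-study visit (main SAP 1.4). The parent interval from end of treatment to end of study is not stated; assume 0-12 weeks. Extra growth per late entrant = velocity × weeks/52.18. At 4-6 cm/year this is 0.9-1.4 cm for 12 weeks and 1.8-2.8 cm for 24 weeks. The effect on the pooled mean depends on how many entered late, which is not given.

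**5. Age mix.** Shift in mean = difference in the share of children in the pubertal spurt × difference in velocity. With 4-5 cm/year before the spurt, 7-9 cm/year in it, and a 10-30 point difference in share:
- smallest: 0.10 × (7 − 5) = 0.2 cm/year
- largest: 0.30 × (9 − 4) = 1.5 cm/year

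This range covers the assumed slowing of 0.5-1.0 cm/year. It describes uncertainty about the expected gain; it is not evidence that the treatment categories differ in age mix.

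**6. Standardised scale.** With an assumed height SD of 6 cm, the slowing is 0.5/6 = 0.08 to 1.0/6 = 0.17 SD. With an assumed SD of one-year z-score change of 0.2-0.3, the half-width is 1.96 × 0.2/√354 = 0.021 to 1.96 × 0.3/√354 = 0.031 SD. A slowing of that size would stand clear of sampling error.

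**7. Japan.** Thirteen children were enrolled, with at least 3 per regimen. The formula in step 2 gives 0.60-1.81 cm at n = 13 and 2.5-7.5 cm at n = 3, so group means there say little on any scale.

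**The case against.** The strongest reply is that growth is not an objective, endpoint, adverse event of special interest or selected adverse-event grouping. It appears once, in the introduction, as a reason to limit steroid use. That stands: a reader might infer that the plan breaks a commitment to measure growth, and the documents contain no such commitment.

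A reader might also infer that slowed growth could not be seen at all, or that only change is tabulated. Neither is supported. Height values are summarised with their spread, and Week 0 is shown separately, so the LTS14424-year gain in means can be read off roughly. Gross slowing would move the mean, clinically significant examination findings are to be reported as adverse events (main SAP 2.1.4.6), and z-scores could be derived later. However, a difference between two visit means is not a paired change with its own SD and CI, and it remains unadjusted for age and sex.

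The two treatment categories do allow a comparison by parent arm over the parent year, among children who rolled over. They give no control for the LTS14424 year, when both receive dupilumab.

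The 104-week criticism does not carry over to Japan, where change starts at the substudy's own baseline.

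Finally, z-scores measure departure from a reference population and cannot say whether steroids, asthma or dupilumab caused it. That also stands, and limits the claim.

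**Conclusion.** The point holds for the main SAP as an optional improvement. The planned height summary is confounded by age and sex, spans about 104 weeks with unequal follow-up, and has no expected value beside it. Modest slowing in the LTS14424 year is therefore unlikely to be recognised. On the assumed velocities and slowing it is about 4-10% of the reported change, against 8-20% of the one-year gain, and comparable with the 0.2-1.5 cm/year that age mix could move the mean.

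These sizes rest wholly on assumed growth rates, slowing and SDs. The absence of a standardised or annualised measure does not; it follows from the SAP text.

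A reader might take Appendix A as already supplying a height reference. It does not: its growth remark, "Based on identification of trends in the child's growth with a series of visits", supports a weight-loss criterion, and the documents do not show whether the sources cited there cover height at these ages.

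**What to change.** In main SAP 2.4.5.4, keep the raw cm table and add:

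1. Height-for-age-and-sex z-score at parent baseline, Week 0 and Week 52, with mean change and 95% CI from Week 0 to Week 52 and from parent baseline. Name one reference in advance. Children aged 6-11 at parent baseline are under 14 about two years later, so it should cover roughly ages 6 to 14.
2. Annualised height velocity from Week 0 to Week 52, using the actual days between measurements, by sex and by the Week 0 age groups in SAP 2.1.1 (7-9, 10 and above).
3. A sentence stating that, with no concurrent control, the result is descriptive and cannot attribute slowing to steroids, asthma or dupilumab.

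For the Japan substudy (n = 13, ages 6 to <12), list individual z-scores at most.

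**Cost.** SAP wording and two derived variables. Birth date (used for age in SAP 2.5.1), sex and height are already held, so no visit or measurement is added and clinical care is unchanged. The real downside is choosing one reference for a multinational sample.

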2.4.5.5 Analyses of electrocardiogram variables

The baseline value of all ECG variables is the original baseline from the parent study. The pre-dose measurement at Week 0 of LTS14424 will be separately presented in the summaries or plots over time.

The summary statistics (including number, mean, median, standard deviation, Q1, Q3, minimum and maximum) of all ECG variables (measurements and changes from baseline) will be calculated for each visit or study assessment (baseline and each post-baseline time point, and endpoint) for each analysis set ([Section 2](#)) of safety population by the treatment category. For all ECG parameters, the mean change from baseline with corresponding standard error at each visit will be plotted by the treatment category for each analysis set of safety population.

For all ECG variables, the summary statistics over visits for either measurements or mean change from baseline, and the plot of mean change from baseline over visits should include the measurements obtained at either scheduled or unscheduled visits.

The incidence of PCSAs (list provided in [Appendix A](#)) at any time during the treatment-emergent adverse event period as defined in [Section 2](#) will be summarized by treatment category for each analysis set of safety population irrespective of the baseline level and/or according to the following status at baseline of parent study and at Week 0 of LTS14424 study, respectively:

- Normal/missing.
- Abnormal according to PCSA criterion or criteria.

For PCSA analyses, the ECG measurements obtained at either scheduled or unscheduled visits should be used.

2.4.5.6 Subgroup analyses

Subgroup analyses will be performed for several key safety variables (treatment-emergent AE/SAE/AESI/AE leading to permanent treatment discontinuation) for full analysis set of safety population by:

- Race (Caucasian/White, Black/of African descent, Asian/Oriental, all the other).
- Sex (Female, Male).
- Ethnicity (Hispanic, Not Hispanic).
- Baseline weight group (≤ 30 , > 30 kg).

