1 OVERVIEW AND INVESTIGATIONAL PLAN

1.1 STUDY DESIGN AND RANDOMIZATION

LTS14424 is a multinational, multicenter, open-label, single arm, 1-year treatment study evaluating dupilumab given subcutaneously (SC) for a period of 52 weeks. The study is designed to evaluate the long-term safety and tolerability of dupilumab in pediatric patients with asthma who participated in a previous dupilumab asthma study (EFC14153). In addition, this study was designed to collect PK, safety, and clinical response information on patients with asthma who weigh ≤ 30 kg and who are treated with dupilumab 300 mg q4w.

Patients receive their first dose of dupilumab in the LTS14424 study at Visit 1 which is Week 0 that corresponds to EOT visit (Week 52) of the parent EFC14153 study. For patients who are not able to perform the EFC14153 EOT visit onsite due to the COVID-19 pandemic, LTS14424 Visit 1 (Week 0) can occur at the EFC14153 EOS visit or for up to 12 weeks after the EFC14153 EOS visit. The initial planned treatment regimen is based on the patients' weight at enrollment in LTS14424: 200mg q2w for children > 30 kg, and 100mg q2w for children ≤ 30 kg. Protocol amendment 3 updated the dose for children ≤ 30 kg to 300 mg q4w, and all children in this weight category with at least 8 weeks remaining before the planned end of treatment period were to be switched to this dose at the time of amendment approval. All newly enrolled children with body weight ≤ 30 kg will take 300 mg q4w. At subsequent visits, for all patients whose body weight increases from ≤ 30 kg to > 30 kg, their dupilumab dose will be increased to 200 mg SC q2w and then maintained during the remaining treatment period.

Approximately 354 patients from parent study (EFC14153) will be enrolled into LTS14424 study.

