2.1 ANALYSIS ENDPOINTS

The baseline values of endpoints in LTS14424 are defined as the original baseline of the parent study, unless otherwise specified. In addition to the baseline, the pre-dose measurements at Week 0 of LTS14424 are defined as the last available measurements prior to the first IMP dose in LTS14424 study.

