2.1.1 Demographic and baseline characteristics

Demographic characteristics

Demographic characteristics are

- Baseline age in years (quantitative and qualitative variable: 6-8, 9-11 years).
- Age in years at Week 0 of LTS14424 (quantitative and qualitative variable: 7-9 years, 10 and above).
- Gender (Male, Female).
- Region (Latin America: Argentina, Brazil, Colombia, Chile and Mexico; Eastern Europe: Poland, Hungary, Romania, Lithuania, Russia, Ukraine and Turkey; Western Countries: Australia, Canada, Italy, South Africa, Spain, and USA).

- Race (Caucasian/White, Black/of African descent, Asian/Oriental, American Indian or Alaska native, Native Hawaiian or other Pacific Islander, Other).
- Ethnicity (Hispanic, Not Hispanic).
- Baseline height in cm.
- Height in cm at Week 0 of LTS14424.
- Baseline weight in kg (quantitative and qualitative variable: weight \leq 30, weight $>$ 30 kg).
- Weight in kg at Week 0 of LTS14424 (quantitative and qualitative variable: weight \leq 30, weight $>$ 30 kg).
- Baseline BMI in kg/m² (quantitative and qualitative variable: BMI $<$ 20, BMI \geq 20 kg/m²).
- BMI in kg/m² at Week 0 of LTS14424 (quantitative and qualitative variable: BMI $<$ 20, BMI \geq 20 kg/m²).

The data for demographic characteristics will be obtained from the original baseline of the parent study.

Medical or surgical history

Medical (or surgical) history includes all the relevant medical (or surgical) history during the lifetime of the patient.

This information will be coded using the version of Medical Dictionary for Regulatory Activities (MedDRA) currently in effect at Sanofi at the time of database locks.

Comorbidity history will be summarized separately. The following comorbid diseases will be summarized.

- Atopic dermatitis history (Yes, Ongoing condition).
- Allergic conjunctivitis history (Yes, Ongoing condition).
- Allergic rhinitis history (Yes, Ongoing condition).
- Allergic conjunctivitis and/or rhinitis history (Yes, Ongoing condition).
- Chronic rhinitis history (Yes, Ongoing condition).
- Chronic sinusitis history (Yes, Ongoing condition).
- Eosinophilic esophagitis history (Yes, Ongoing condition).
- Food allergy history (Yes, Ongoing condition).
- Hives history (Yes, Ongoing condition).

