2.4.7 Analyses of Immunogenicity

The baseline value used to define ADA variables is the original baseline from the parent study. The ADA analyses will be performed for each analysis set ([Section 2](#)) of ADA population ([Section 2.3.4](#)) by treatment category.

The ADA variables described in [Section 2.1.6](#) will be summarized using descriptive statistics. Frequency tables of the proportion of patients developing ADA positivity in the ADA assay, neutralizing antibody status in the NAb assay, pre-existing immunoreactivity, treatment-emergent, treatment-boosted, persistent, indeterminate, transient ADA responses and titers will be presented.

Listing of all ADA maximum titer levels and neutralizing antibody status will be provided for ADA positive patients.

ADA variable will be summarized by baseline weight group (≤ 30 , > 30 kg).

If there were patients who had a long gap between the parent EOT visit and the first dose in LTS14424 study, additional analyses excluding such patients may be conducted for the status in the ADA assay in the current study on the full analysis set of ADA population.

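### The safety and ADA weight subgroups use parent-study baseline weight, so children who passed 30 kg before entry start on 200 mg q2w but are reported in the group at or below 30 kg

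*SAP*

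**What the plan says.** **Subgroup variable.** Main SAP 2.4.5.6 plans subgroup tables of treatment-emergent AEs, SAEs, AESIs and AEs leading to discontinuation "for full analysis set of safety population by" race, sex, ethnicity and "Baseline weight group", cut at 30 kg. SAP 2.4.7 states: "ADA variable will be summarized by baseline weight group", with the same cut.

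**Meaning of baseline.** SAP 2.1: "The baseline values of endpoints in LTS14424 are defined as the original baseline of the parent study, unless otherwise specified". SAP 2.1.1 adds: "The data for demographic characteristics will be obtained from the original baseline of the parent study". Sections 2.4.1, 2.4.5 and 2.4.7 repeat the rule for demographics, safety parameters and ADA. Nothing in 2.4.5.6 or 2.4.7 specifies otherwise for weight.

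**A second weight variable.** SAP 2.1.1 also lists "Weight in kg at Week 0 of LTS14424", with the same 30 kg categories. Neither subgroup uses it.

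**Dosing.** SAP 1.1 bases the initial regimen on "weight at enrollment in LTS14424: 200mg q2w for children" above 30 kg, and 100 mg q2w (later 300 mg q4w) at or below 30 kg. Protocol 8.4 also assigns by weight at the enrolment visit. Protocol 10.1.1 moves a child who passed 30 kg during the parent study to 200 mg q2w at Visit 1.

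**The concern.** The subgroup is cut where the dosing rule is cut, but at a different time. Week 0 of LTS14424 is Week 52 of the parent study, or later for patients who entered late because of COVID-19. These are growing children, so some at or below 30 kg at parent baseline will be above it at Week 0. They receive 200 mg q2w from the first dose of this study and are still tabulated in the lighter group.

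This matters because the main SAP reports safety by parent-study treatment category (2.4) and presents only PK by regimen (2.4.6.1). The weight subgroup is the only planned safety split that approximates 100 mg versus 200 mg exposure. If a TEAE or AESI difference between those exposures existed, misplaced children would tend to blur it.

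The mismatch is clearest for Placebo-Dupilumab patients. Their first dupilumab dose is given in LTS14424, so parent-baseline weight never set a dupilumab dose they received.

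**Working it through.** **1. The plan's own figure.** SAP 1.3 expects about 354 patients, 87% of 408: 0.87 × 408 = 354.96. This reproduces and is used below only for scale.

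**2. Gap between the two weights.** Same-day roll-over: about 52 weeks (SAP 1.1). Late entry is allowed up to 12 weeks after the parent end-of-study visit. The documents do not give the week of that visit; if it is Week 64, the longest gap is 64 + 12 = 76 weeks.

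**3. Who is placed where.**

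| Parent baseline | LTS14424 Week 0 | Starting regimen | Reported group |
|---|---|---|---|
| ≤30 kg | ≤30 kg | 100 mg q2w or 300 mg q4w | ≤30 kg |
| ≤30 kg | >30 kg | 200 mg q2w | ≤30 kg |
| >30 kg | >30 kg | 200 mg q2w | >30 kg |

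The second row is the problem. The reverse case needs a child to fall back to 30 kg or less within the year, which should be rare.

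The protocol's Clinical Trial Summary words the change to 200 mg as something that can happen. Protocol 8.1.1, 8.4 and 10.1.1 word it as something that will happen, and SAP 2.2.1 counts 100 mg or 300 mg dispensed above 30 kg as an irregularity. The table follows the body text; the two wordings should be reconciled.

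**4. Whether another planned safety table does this job.** The modified analysis set (SAP 2) drops data from the first 300 mg q4w dose onward. It keeps 100 mg and 200 mg q2w together, so it does not separate these two. The safety subgroups run on the full analysis set only.

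**5. Scale, on assumptions.** The documents give no weight distribution or growth rate. Assume parent-baseline weight is normal with mean m and SD s, truncated below 15 kg, with a constant gain g before Week 0. Then

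share above 30 kg at Week 0, among those ≤30 kg at parent baseline = [Φ((30−m)/s) − Φ((30−g−m)/s)] / [Φ((30−m)/s) − Φ((15−m)/s)].

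For m = 28, 32, 36 kg, s = 7, 9, 11 kg and g = 2, 3, 4 kg:

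- Lowest (m = 28, s = 11, g = 2): (0.572 − 0.500)/(0.572 − 0.119) = 0.159.
- Middle (m = 32, s = 9, g = 3): (0.412 − 0.289)/(0.412 − 0.029) = 0.321, about 45 of 140 children.
- Highest (m = 36, s = 7, g = 4): (0.1957 − 0.0766)/(0.1957 − 0.0013) = 0.613.

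The range is about 16% to 61%. Applied to 354 patients, the grid gives about 22 to 82 children misplaced relative to their starting regimen. The smallest and largest counts come from different settings than the smallest and largest shares, because the size of the lighter group also changes.

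**The case against.** The strongest reply is that nothing here is an error. Parent baseline is the SAP's stated reference throughout, and the efficacy subgroups also use parent-baseline ICS dose, eosinophils, FeNO and age. Section 2.4.5.6 lists weight beside race, sex and ethnicity and does not call it a dose subgroup. This stands: the choice follows the SAP's own rule, and the point concerns interpretability. The SAP does, however, use Week 0 status where it helps, since PCSA incidence is tabulated by status at parent baseline and at Week 0 (2.4.5.3 to 2.4.5.5).

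For ADA the parent-baseline cut has a reason. Treatment-emergent and treatment-boosted responses are judged against the parent baseline (2.1.6). For Dupilumab-Dupilumab patients, parent-baseline weight relates to the regimen on which exposure began (Protocol 4.2). This also stands, so that split should not be dropped.

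Week 0 weight does not cure the mixing. Children at or below 30 kg at Week 0 may be on 100 mg q2w or 300 mg q4w, and may move to 200 mg q2w on passing 30 kg during LTS14424. Take normal weights without truncation (mean/SD 33/8, 35/10 or 37/11 kg) and a gain of 2 to 4 kg in each year. Then 21% to 46% of the parent-baseline lighter group pass 30 kg before Week 0. Of the Week 0 lighter group, 23% to 56% pass it during the next 52 weeks: [Φ((30−g−m)/s) − Φ((30−2g−m)/s)] / Φ((30−g−m)/s), for example (0.191 − 0.085)/0.191 ≈ 0.56 for m = 33, s = 8, g = 4. Those later crossers spend only part of the year on 200 mg, so the mixing is reduced but not removed. SAP 1.6 describes the number exposed to 300 mg q4w as very limited, which restricts that source.

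**Conclusion.** The point holds as a cheap improvement. The reading of baseline and the dosing rule are clear in the documents, so the misplacement of children who passed 30 kg in the parent year follows directly. Its size does not: 16% to 61% rests wholly on the assumed weights and growth in the working.

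A reader might infer more than the documents support:

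- That the subgroup no longer separates the regimens. The group above 30 kg stays essentially on 200 mg q2w; the contamination is in the lighter group.
- That no other safety analysis relates to regimen. The modified analysis set does, although it cannot distinguish 100 mg from 200 mg.
- That a real safety or ADA difference is being hidden. Nothing in the documents shows that one exists.
- That the primary result is affected. It is not: overall TEAE incidence does not depend on the weight split, all safety analyses are descriptive, and sample size and error rates are not involved.

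The Japan substudy is also unaffected. Its SAP takes baseline as the last value before the first dose, and its regimen is fixed at baseline.

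**What to change.** - In SAP 2.4.5.6, define the weight subgroup by weight at Week 0 of LTS14424 (≤30, >30 kg), and make the same change in the safety table of Appendix B.
- In SAP 2.4.7, add the Week 0 weight split and keep the parent-baseline split, which remains relevant for Dupilumab-Dupilumab patients.
- State in both sections that the group at or below 30 kg will still include 300 mg q4w patients and children who move to 200 mg q2w during LTS14424, so the split reduces regimen mixing but does not remove it.

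The cost is a few extra tables and a departure from the parent-baseline convention for this one variable. The variable and its categories already exist in 2.1.1, so no new data or procedure is needed. Parent-baseline weight stays in the demographics table.
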